8.4. Deaths

If any patient dies during the study, a listing of deaths will be provided, and all relevant information will be discussed in the patient narrative included in the clinical study report.

8.5. Clinical Laboratory Tests

Clinical laboratory tests (serum chemistry, hematology and coagulation, and urinalysis) will be performed using the central laboratory at the time points detailed in the study protocol. Specific laboratory tests to be performed are listed below in Table 5.

Serum chemistry	Hematology and co	agulation	Urinalysis	
Calcium	Hemoglobin		Protein	
Phosphate	Hematocrit		Glucose	
Sodium	Erythrocytes		Ketones	
Potassium	Platelets		Hemoglobin	
Chloride	Leucocytes		pН	
Creatinine	 Neutrophils 		Specific gravity	
Glucose	_	Lymphocytes	Microscopic tests	
BUN	_	Eosinophils	-	Bacteria
LDL	_	Monocytes	-	Erythrocytes
HDL	_	Basophils	_	Leucocytes
Triglycerides	Lymphocytes atypic	al	_	Crystals
Urate	Prothrombin INR		-	Casts
ALT				
AST				
LDH				
GGT				
ALP				
Bicarbonate				
Carbon dioxide				
Protein				
Albumin				
Bilirubin				
Direct bilirubin				

Table 5: Clinical Laboratory Tests

ALP=alkaline phosphatase; ALT=alanine aminotransferase; AST=aspartate aminotransferase; BUN=blood urea nitrogen; GGT=gamma glutamyl transpeptidase; HDL=high-density lipoprotein; INR=international normalized ratio; LDH=lactate dehydrogenase; LDL=low-density lipoprotein.

Laboratory test results will be presented in standard international (SI) units.

Summary statistics for chemistry, hematology, urinalysis, and coagulation laboratory tests will be presented at baseline, weeks 0, 8, 12 for double-blind and week 24 for open-label, and last on study assessment for both periods. Laboratory values and changes from baseline to each visit and last on study assessment will be summarized using descriptive statistics. Shifts (below, within, and above the normal range) from baseline to each visit and last on study assessment will be summarized using descriptive statistics is such as the normal range of all individual patients' laboratory test results will be presented.

All clinical laboratory test results outside of the reference range will be judged by the investigator as belonging to one of the following categories:

- abnormal and not clinically significant
- abnormal and clinically significant

A laboratory test result that is judged by the investigator as clinically significant will be recorded both on the source documentation and the CRF as an adverse event. The incidence of potentially

clinically significant abnormal results will be summarized using descriptive statistics with the criteria specified in Table 6. The potentially clinically significant abnormal laboratory values will include all postbaseline values (including scheduled, unscheduled, and early termination visits) for the summaries. Listings of patients who have potentially clinically significant abnormal laboratory data will be presented.

Test	Criterion value
Serum chemistry	
Alanine aminotransferase (ALT)	≥3x ULN
Aspartate aminotransferase (AST)	≥3x ULN
Alkaline phosphatase	≥3x ULN
Gamma-glutamyl transpeptidase (GGT)	≥3x ULN
Lactate dehydrogenase (LDH)	≥3x ULN
Blood urea nitrogen (BUN)	≥10.71 mmol/L
Creatinine	≥177 μmol/L
Uric acid Men	≥625 μmol/L
Women	≥506 μmol/L
Bilirubin (total)	$\geq 2x$ ULN
Potassium	\leq 3 mmol/L or \geq 6 mmol/L
Calcium	\leq 1.5 mmol/L or \geq 3.5 mmol/L
Hematology and Coagulation	
Hematocrit Men	<0.37 L/L
Women	<0.32 L/L
Hemoglobin Men	≤115 g/L
Women	≤95 g/L
White blood cell (WBC) counts	$\leq 3 \ge 10^{9}/L$
	$\geq 20 \text{ x } 10^9/\text{L}$
Eosinophils	≥10%
Absolute neutrophil counts (ANC)	$\leq 1 \times 10^{9}/L$
Platelet counts	$\leq 75 \text{ x } 10^9/\text{L}$
	\geq 700 x 10 ⁹ /L
INR	\geq 1.5x ULN
Urinalysis	
Blood (HGB)	≥2 unit increase from baseline
Glucose	≥2 unit increase from baseline
Ketones	≥2 unit increase from baseline
Total protein	≥2 unit increase from baseline

HGB=Hemoglobin; INR=International Normalized Ratio; ULN=upper limit of normal range.

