 - j. Participation in a clinical study of a new chemical entity or a prescription medicine within 2 months before screening (visit 1) (or 3 months in the case of a biologic if the half-life of the biologic is unknown) or 5 half-lives, whichever is longer, or is currently participating in another study of an IMP or medical device.
 - k. Any prior exposure to a mAb targeting the CGRP pathway (erenumab, eptinezumab, galcanezumab, or fremanezumab) during the 6 months before the screening visit (visit 1), or exposure to gepants for less than 5 half-lives before screening.
 - l. Any finding in the baseline 12-lead ECG considered clinically significant in the judgment of the investigator.
 - m. Any finding that, in the judgment of the investigator, is a clinically significant abnormality, including physical examination findings, and serum chemistry, hematology, coagulation, and urinalysis test values (abnormal test results may be repeated for confirmation).
 - n. Hepatic enzymes (alanine aminotransferase [ALT], aspartate aminotransferase [AST], and alkaline phosphatase [ALP]) $>2\times$ the upper limit of normal (ULN) after confirmation in a repeat test or suspected hepatocellular damage that fulfills criteria for Hy's law at screening (visit 1).
 - o. Serum creatinine $>1.5\times$ ULN, clinically significant proteinuria, or evidence of renal disease at screening (visit 1).
 - p. Any clinically significant uncontrolled medical condition (treated or untreated).
 - q. History of alcohol or drug abuse during the past 2 years or drug dependence during the past 5 years.

- r. The patient cannot participate or successfully complete the study, in the opinion of his/her healthcare provider or the investigator, for any of the following reasons:
 - mentally or legally incapacitated or unable to give consent for any reason
 - in custody due to an administrative or a legal decision, under tutelage, or being admitted to a sanitarium or social institution
 - unable to be contacted in case of emergency
 - has any other condition that, in the opinion of the investigator, makes the patient inappropriate for inclusion in the study
- s. The patient is a study center or sponsor employee who is directly involved in the study or the relative of such an employee.
- t. The patient has any disorder that may interfere with the absorption, distribution, metabolism, or excretion of the IMP.

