4.2. Specification of Baseline Values

Patients will complete electronic headache diary entries daily for the 28-day run-in period, subjectively rating their headaches as mild, moderate, or severe and enter headache information about the previous day into the electronic headache diary device. If the run-in period is greater or less than 28 days, the baseline values for calculating the change from baseline of the monthly values of the efficacy variables will be prorated to **28** days.

The efficacy baseline values during the 28-day run-in period derived from the electronic headache diary device include

- total number of migraine days
- total number of days of use of any acute headache medications (as collected in the daily diary ie. in addition to randomized treatment)
- total number of headache days of at least moderate severity
- total number of headache days of any severity
- total number of headache hours of at least moderate severity
- total number of days with nausea or vomiting
- total number of days with photophobia and phonophobia
- total number of days of use of migraine-specific acute headache medications (triptans and ergot compounds)

Otherwise baseline value will be the last non-missing value prior to the 1st dose of study drug, unless otherwise noted.

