8.7. Vital Signs

Vital signs (blood pressure [systolic/diastolic], respiratory rate, body temperature, and pulse) will be measured at every visit including unscheduled visits.

For any abnormal vital sign finding, the measurement should be repeated as soon as possible. Any vital sign value that is judged by the investigator as a clinically significant change (worsening) from a baseline value will be considered an adverse event.

Vital signs values and changes from baseline to each visit and endpoint will be summarized using descriptive statistics and vital signs values will be listed.

Table 7 specifies the criteria for identifying vital signs as potentially clinically significant abnormal values. Note that in order to be identified as potentially clinically significant abnormal, a value would need to meet both conditions below: i.e., have a value beyond the criterion value and a change of at least the magnitude specified in the change from baseline column. The

potentially clinically significant abnormal vital signs values will include all postbaseline values (including scheduled, unscheduled, and early termination visits) for the summaries. The incidence of potentially clinically significant values will be both listed and summarized using descriptive statistics.

Vital Sign	Criterion value	Change relative to baseline
Pulse	≥120 bpm	Increase of ≥15 bpm
	≤50 bpm	Decrease of ≥15 bpm
Systolic blood pressure	≥180 mm Hg	Increase of ≥20 mm Hg
	≤90 mm Hg	Decrease of ≥20 mm Hg
Diastolic blood pressure	≥105 mm Hg	Increase of ≥15 mm Hg
	≤50 mm Hg	Decrease of ≥15 mm Hg
Respiratory rate	<10 breaths/min	
Body temperature	≥38.3°C	Change of ≥1.1°C

Table 7: Criteria for Potentially Clinically Significant Vital Signs

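### SAP 8.5 counts blood-test abnormalities already present before the first dose as on-treatment incidence, because the Table 6 limits for chemistry, hematology and coagulation ignore baseline

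*SAP*

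**What the plan says.** SAP 8.5 states that the incidence of potentially "clinically significant abnormal results will be summarized using descriptive statistics with the criteria specified in Table 6". On which values count, it says: "The potentially clinically significant abnormal laboratory values will include all postbaseline values (including scheduled, unscheduled, and early termination visits) for the summaries". In Table 6, every chemistry, hematology and coagulation row is a fixed number or a multiple of the upper limit of normal (ULN); for example, hemoglobin in women is flagged at 95 g/L or below. No row in those panels refers to the patient's own baseline. Section 8.5 defines no denominator of patients free of the abnormality at baseline.

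Elsewhere the SAP does use baseline. The urinalysis rows of Table 6 require "≥2 unit increase from baseline". For vital signs, SAP 8.7 requires that a value "have a value beyond the criterion value and a change of at least the magnitude specified in the change from baseline column"; only respiratory rate in Table 7 has no change entry.

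A laboratory baseline is already defined, in SAP 4.2: "Otherwise baseline value will be the last non-missing value prior to the 1st dose of study drug". The categorical display in 8.5 that uses it is the shift table: "Shifts (below, within, and above the normal range) from baseline to each visit and last on study assessment will be summarized". Protocol 9.7 compares all values with predefined criteria and adds no baseline condition. Protocol 7.4 leaves the criteria to the SAP.

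**The concern.** A table labelled incidence should show events that arise after treatment starts. Under this rule it mixes new events with abnormality that was already there. Take a woman with a predose hemoglobin of 94 g/L, judged not clinically significant by the investigator, and the same value at week 8. She enters the table as an on-treatment case although nothing has changed.

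In the double-blind period randomization should make this background similar in the two arms, so it adds to both percentages. In the open-label period everyone receives fremanezumab and no concurrent placebo column shows how much is background. A long-standing low hemoglobin or high eosinophil count then reads as something that occurred on drug. Laboratory results are a named safety endpoint and the study has no data monitoring committee, so these summaries carry weight.

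**Working it through.** **Step 1: which tests are exposed.** Set the entry criteria in Protocol 4.2 beside the Table 6 limits.

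- ALT, AST, ALP: exclusion n removes values above 2x "the upper limit of normal (ULN) after confirmation in a repeat test". The Table 6 limit is 3x ULN or more. A pre-existing case would need a further rise between screening and the predose sample at visit 2, so these tests are largely protected.
- Creatinine: exclusion o removes values above 1.5x ULN, while Table 6 uses 177 μmol/L. The ULN is not given, so the protection cannot be sized.
- Bilirubin: it enters exclusion n only through Hy's law; raised bilirubin alone has no numeric entry limit.
- Hemoglobin, hematocrit, WBC, eosinophils, neutrophils, platelets, INR, urate, GGT, LDH, BUN, potassium, calcium: no numeric entry limit. Exclusion m applies only if the investigator judges the finding clinically significant.

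**Step 2: whether another display separates new from pre-existing.** The shift tables use the normal range. A patient below normal at both times is shown as below to below, whether or not the Table 6 limit was crossed in between. Change-from-baseline summaries describe groups. The listings allow a patient-by-patient check but leave the incidence table as it is.

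**Step 3: size.** The documents state no rate of such abnormalities, so there is no figure of the plan's to reproduce and the inputs are assumptions:

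- b, share of patients past the limit at baseline, equal in both arms: 1% and 3%.
- p, new-onset incidence among the rest: p0 = 1% placebo, p1 = 3% fremanezumab (difference 2.00 points, ratio 3.0).
- s, share of baseline-abnormal patients past the limit again at any postbaseline sample.

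Reported incidence = b·s + (1 − b)·p. The risk difference is therefore (1 − b)(p1 − p0), which does not depend on s.

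With full persistence (s = 100%):

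- b = 1%: placebo 0.01 + 0.99 × 0.01 = 1.99%; drug 0.01 + 0.99 × 0.03 = 3.97%. Difference 1.98 points, ratio 1.99. Of 186 patients per group, that is 3.7 vs 7.4, against 1.9 vs 5.6 with b = 0.
- b = 3%: placebo 0.03 + 0.97 × 0.01 = 3.97%; drug 0.03 + 0.97 × 0.03 = 5.91%. Difference 1.94 points, ratio 1.49. That is 7.4 vs 11.0 of 186.

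Full persistence is the upper bound. For a range, take an equicorrelated normal model for one baseline and two postbaseline samples, with within-patient correlation 0.5 to 0.9. Two postbaseline samples match the SAP 8.5 schedule for the double-blind period, "presented at baseline, weeks 0, 8, 12 for double-blind and week 24 for open-label", since week 0 is predose under Protocol Table 3. Simulation (4 million draws) gives s of about 22% to 69% at b = 1% and about 32% to 75% at b = 3%. The ratios become:

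- b = 1%: (0.0022 + 0.0297)/(0.0022 + 0.0099) ≈ 2.6, down to (0.0069 + 0.0297)/(0.0069 + 0.0099) ≈ 2.2.
- b = 3%: (0.0096 + 0.0291)/(0.0096 + 0.0097) ≈ 2.0, down to (0.0225 + 0.0291)/(0.0225 + 0.0097) ≈ 1.6.

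In the same model with no drug effect, the share of counted patients who were already past the limit at baseline, at correlation 0.5, 0.7 and 0.9, is 12%, 23% and 47% at 1% prevalence, and 18%, 30% and 53% at 3%.

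**The case against.** A reader might infer that the rule dilutes the drug–placebo contrast enough to hide a laboratory signal. The documents do not support that. SAP 8.1 and 8.5 plan counts and percentages; no ratio or test is specified for these results. Two percentages side by side are naturally compared by their difference, which shrinks only by the factor (1 − b). The marked movement is on the ratio scale, and its lowest values assume that every baseline-abnormal patient stays past the limit.

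The assumed prevalence may also be high. Many limits are extreme (3x ULN, platelets at or below 75 × 10⁹/L, neutrophils at or below 1 × 10⁹/L), and patients must be in good health with no laboratory finding judged clinically significant. If only 1 of 372 patients were past a limit at baseline (b ≈ 0.27%), even full persistence leaves a ratio of about 2.6 and a difference of 1.99 points.

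The shift tables give partial help: where a limit lies outside the normal range, a stable pre-existing case appears as abnormal to abnormal rather than as a new shift. An all-values count can also be defended as an inclusive screen, and dropping already-abnormal patients from the table would hide worsening, such as GGT rising from 3x to 10x ULN.

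All of this stands, and it limits the consequence and shapes the remedy. It leaves the core untouched: the table is called incidence and does not distinguish new from pre-existing.

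**Conclusion.** The point holds as a defect in a descriptive safety table and is worth correcting. As written, SAP 8.5 counts stable pre-existing chemistry, hematology and coagulation abnormality as on-treatment incidence, without a stated reason for departing from the SAP's own practice for urinalysis and most vital signs. The robust harm is inflated absolute incidence, most misleading in the open-label period. In the double-blind period the between-arm difference is nearly intact on the assumed rates, while a ratio read off the table would be pulled toward 1. No planned test or error rate changes. The sizes rest on assumed new-onset rates, assumed prevalence equal in both arms, and a persistence model; true prevalence will differ by test and may be near zero for the extreme limits.

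**What to change.** In SAP 8.5, present each Table 6 chemistry, hematology and coagulation criterion by baseline status, met or not met at the last predose value as defined in SAP 4.2.

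- Compute treatment-emergent incidence among patients who did not meet the criterion at baseline and have at least 1 postbaseline value. On the assumed inputs this recovers 1% vs 3%.
- Show patients who met it at baseline in a separate row with their worst postbaseline status, so that worsening stays visible.
- Keep the all-values count and the listing, so that no patient drops out of view.

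The cost is one derived flag and some extra table rows. No new data are needed.

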8.5.1. Laboratory Values Meeting Hy's Law Criteria

All occurrences of possible drug-induced liver injury that meet Hy's law criteria as defined in the protocol will be included in adverse events reporting.

8.5.2. Other Clinical Laboratory Tests

8.5.2.1. Human Chorionic Gonadotropin Test

Serum beta-human chorionic gonadotropin (β -HCG) tests will be performed for all women of childbearing potential at screening (visit 1) and visit 8. Urine pregnancy tests will be performed for all women of childbearing potential at visit 2 to 7 and the EOT/early termination visit. Pregnancy test results will be listed.

8.5.2.2. Follicle-Stimulating Hormone Test

Postmenopausal women will have a follicle-stimulating hormone (FSH) test at screening. Results will be listed.

8.6. Physical Examinations

Physical examinations, including height (to be measured at the screening visit only) and weight will be performed at screening, weeks 0, 4, 8, 12, 24 and last on study assessment.

A complete physical examination will include the following organ systems: general appearance; head, eyes, ears, nose, and throat; chest and lungs; heart; abdomen; musculoskeletal; skin; lymph nodes; and neurological. Any physical examination finding that is judged by the investigator as a potentially clinically significant change (worsening) compared with a baseline value will be considered an adverse event and recorded on the CRF, and monitored as described in the study protocol. Abnormal findings at baseline will be summarized by treatment group using patient counts. Shifts from baseline to weeks 4, 8, 12 for double-blind and week 24 for open-label and last on study assessment for both periods will be summarized using patient counts. Listings of findings for all physical examinations will be presented.

Descriptive statistics for weight and height will be provided.

8.7. Vital Signs

Vital signs (blood pressure [systolic/diastolic], respiratory rate, body temperature, and pulse) will be measured at every visit including unscheduled visits.

For any abnormal vital sign finding, the measurement should be repeated as soon as possible. Any vital sign value that is judged by the investigator as a clinically significant change (worsening) from a baseline value will be considered an adverse event.

Vital signs values and changes from baseline to each visit and endpoint will be summarized using descriptive statistics and vital signs values will be listed.

Table 7 specifies the criteria for identifying vital signs as potentially clinically significant abnormal values. Note that in order to be identified as potentially clinically significant abnormal, a value would need to meet both conditions below: i.e., have a value beyond the criterion value and a change of at least the magnitude specified in the change from baseline column. The

potentially clinically significant abnormal vital signs values will include all postbaseline values (including scheduled, unscheduled, and early termination visits) for the summaries. The incidence of potentially clinically significant values will be both listed and summarized using descriptive statistics.

Vital Sign	Criterion value	Change relative to baseline
Pulse	≥120 bpm	Increase of ≥15 bpm
	≤50 bpm	Decrease of ≥15 bpm
Systolic blood pressure	≥180 mm Hg	Increase of ≥20 mm Hg
	≤90 mm Hg	Decrease of ≥20 mm Hg
Diastolic blood pressure	≥105 mm Hg	Increase of ≥15 mm Hg
	≤50 mm Hg	Decrease of ≥15 mm Hg
Respiratory rate	<10 breaths/min	
Body temperature	≥38.3°C	Change of ≥1.1°C

Table 7: Criteria for Potentially Clinically Significant Vital Signs

8.8. Electrocardiography

A single 12-lead ECG will be performed at screening, week 0, 8, 24, and at visit 9 (follow-up) if assessment at visit 8 (EOT/ET) shows abnormality. This procedure will be performed predose.

All ECG results outside of the reference ranges will be judged by the investigator as belonging to one of the following categories:

- abnormal and not clinically significant
- abnormal and clinically significant

If results are abnormal, the ECG will be repeated 1 time.

Summary of ECG findings (normal, abnormal not clinically significant and abnormal clinically significant) will be presented at baseline. Shifts in ECG finding (normal, abnormal not clinically significant and abnormal clinically significant) from baseline to overall result interpretation, week 8 for double-blind and week 24 for open-label and last on study assessment (double-blind and open-label) will be summarized using patient counts. For overall result interpretation the worst post baseline finding for the patient (the abnormal finding if there are both normal and abnormal findings) will be used in the summaries. Actual values and changes from baseline to each visit and last on study assessment (for both double-blind and open-label periods) will be summarized using descriptive statistics. Both result interpretation and values will be listed.

Any ECG finding that is judged by the investigator as a potentially clinically significant change (worsening) compared with the baseline value will be considered an adverse event.

8.9. Concomitant Medications or Therapies

Any concomitant therapy, medication or procedure up to the end of the study period will be recorded on the CRF. Generic or trade name, indication, and dosage will be recorded. The

sponsor will encode all therapy and medication according to the World Health Organization Drug Dictionary (WHODrug) version 2023MAR01DDE or higher.

Up to 30% of patients will be allowed to remain on stable doses of no more than 1 preventive migraine medication presented in the study protocol (in addition to other medications not listed in the study protocol) for the duration of the study. Patients on preventive medication must be on a stable dose for at least 2 months of consecutive use prior to screening with no expectation to change dosing regimen or change to another migraine preventive medications during the treatment phase of the study.

Patients will be allowed to use acute medication to treat breakthrough migraines as needed, with the exception of medications containing opioids and barbiturates, which cannot be used on more than 4 days during the screening period. Traditional Chinese therapy (including herbal medicine) and acupuncture are allowed if the patient is on a stable dosing regimen for at least 2 months (consecutive) before screening.

Concomitant medications will be listed by double-blind treatment group. The incidence of concomitant medications will be summarized using descriptive statistics by therapeutic class and PT. Patients are counted only once in each therapeutic class category, and only once in each PT category. Concomitant medications will include all medications taken while the patient is treated with the IMP.

The subset of concomitant pain medication and medication or therapy for migraine/headache will also be summarized by the following indication categories:

- butalbital for migraine/headache
- ergots for migraine/headache
- NSAIDs for migraine/headache
- NSAIDs for other reason than migraine/headache
- opioids for migraine/headache
- opioids for reasons other reason than migraine/headache
- preventive medication from protocol Appendix K for migraine/headache
- preventive medication from protocol Appendix K for other reason than migraine/headache
- triptans for migraine/headache

